## **9.0 LABORATORY SPECIMENS AND BIOHAZARD CONTAINMENT**

### **9.1 Local Laboratory Specimens**

As described in Section 5, rapid HIV test will be done during the Screening visit to confirm the HIV-negative status of the participant. The rapid test will be done using test kits routinely by the community centers providing HIV prevention services, by the study nurse.

At Enrollment, a venous blood sample will be collected to perform the creatinine test. The specimen will be collected at the clinical sites and processed at the local site laboratories (LL).

At Enrolment, Month 3 and 6 visits, DBS samples will be collected for pharmacology testing. Both samples will be stored in a -20° C freezer at the LL. The specimens will be analyzed in batches at the end of the study, and will not be used for adherence counseling during this study. Data from individual study participants will not be returned to study sites or study participants. TDF will be quantified with a validated liquid chromatography tandem mass spectrometry method. The specimens of participants who do not consent to long-term storage and additional testing will be destroyed at the end of the study.

Each study site will adhere to standards of good clinical laboratory practice, and SOP for specimen management including proper collection, processing, labeling, transport, and storage of specimens to the LL.

## **10.0 DISSEMINATION AND REPORTING**

### **10.1 Notifying Participants of Study Findings**

Written material summarizing the findings from this study will be made available to participants and study staff upon completion of the study. The exact type of material is to be determined; usual forms of written communication targeting PWID in Ukraine are posters and brochures.

### **10.2 Dissemination of Study Findings**

The study findings will be disseminated through presentations and publications in peer reviewed journals and other publications. Reports will be disseminated to an international audience, as well as to national and local HIV prevention planning groups who may use the findings to assist in the creation of HIV prevention activities. The UIPHP publications and presentations policy will be utilized.

In-country data and country-specific information will be made available to national policy-makers, organizations, and implementing partners as soon as possible. Study staff will be notified of the findings upon their presentation or publication. Any formal presentations at conferences or scientific publications will follow UIPHP procedures for publications and presentations.

**APPENDIX I - SCHEDULE OF EVALUATIONS AND PROCEDURES**

	Pre-screening	Enrollment	Month 1, 3	Month 2,4,5 (by phone)	Month 6 (exit)	Interim visits
Administrative and Behavioral Evaluations/ Procedures						
Pre-screening	x					
Eligibility screening and demographic information		x				
Informed Consent, randomization		x				
Locator information		x	x	x		x
Behavioral and psychosocial survey		x	x		x	
Initial PrEP adherence readiness assessment (PN)		x				
Self-reported study product adherence assessment (PN)			x	x	x	x
Individual Interview for selected participants						x
Staff Focus Group (after all participants complete)						x
Intervention provision						
PrEP Discussion		x	x	x	x	x
Autonomy Supportive Adherence Counseling		x	x	x		x
PrEP Navigation and study product supply		x	x			x
SMS reminder customization 		x	x	x		x
SMS reminder 		x	xx	xx		
HIV/ STI behavioral risk-reduction counseling		x	x		x	x
Provision of prevention supplies		x	x		x	x
Clinical Evaluations/ Procedures						
Medical history including medications		x				
Symptom-Driven Physical Examination		x				
Laboratory Evaluations/Procedures						
HIV screening testing		x	x 		x	
HBsAg testing		x			x	
Renal function tests (creatinine)		x				
Calculated creatinine clearance		x				
DBS storage for possible Pharmacology testing		x	x		x	

 Experimental arm only.

 Month 3 only

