#### **2. Informed consent**

Prior to screening, every potential participant demonstrating interest in study participation will have to sign the Informed Consent Form (See Appendix III). Consent procedure will be performed by a study staff member responsible for recruitment. In more details, the consent procedure is described in Section 8.

3. Randomization

Consenting participants will be randomized using the functionality in REDCap participant database using a pre-defined allocation schedule stratified by site.

4. Locator information

After signing the ICF, the participant will provide his contact information. Staff members will assure participants that the detailed follow-up information will be deleted if they are not enrolled in the study.

5. Behavioral and psychosocial survey

Structured interviews will be administered by an experienced interviewer using the questionnaire designed by study team (Appendix II). Baseline and follow-up questionnaires will not differ in content. Interview data will be directly entered into the online version of the participant questionnaire at the REDCap platform.

*Intervention provision (intervention staff)*

6. Assess participant's readiness for PrEP adherence

PNs will use a PrEP readiness tool to assess key predictors of PrEP adherence.

7. PrEP discussion

PrEP Education will be provided at each study visit to participants by PrEP Navigators with the option to start/continue, stop, or abstain from usage. A manual will be created for all sites to follow when discussing PrEP with participants based on safety and efficacy language found in the ICF under "Study Purpose".

8. Autonomy supportive adherence counseling

Adherence counseling will be provided to all participants who initiate PrEP at each study visit starting at the enrollment visit. The counseling makes use of self-determination theory that is designed to facilitate the client's integration of PrEP usage into his health behavioral routines and support the client in making his own decisions regarding adherence. Counseling will include the development of client-centered strategies to support the consistent daily adherence of PrEP. This counseling is delivered one-on-one by PrEP navigators during the study visits. The counseling will also include reminders not to share the medication and to contact project staff with questions about product use.

After each counseling session, the PN will fill out the Care Coordination Measurement Tool (CCMT).

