### 5.3 Month 1, 3 and Month 6 (exit visit)

At months 1 and 3, the participants will visit the clinical site to complete the assessments and receive the medication supply for next two (at month 1) three (at month 3) months. At month 6, participants will not receive medication as a part of the study, but will be referred to other available PrEP providers in Kyiv. The following procedures will be included.

- Verify locator information
- Behavioral and psychosocial survey
- Self-reported study product adherence assessment
- PrEP discussion
- PrEP Navigation and study product supply
- Autonomy supportive adherence counseling
- SMS reminder customization

- HIV/ STI behavioral risk-reduction counseling, provision of prevention supplies
- Medical history including but not limited to co-morbidities, concomitant medications, HIV risk history
- Symptom-driven physical exam
- AE Assessment
- HIV rapid test – at months 3 and 6.
- DBS storage for pharmacology testing
- Urine storage for substance use testing

The exit visit will include all procedures for Month 3, except for PrEP provision and related counseling and SMS customization.

#### 5.4 Months 2, 4, 5

Monthly assessments between the PrEP dispensing visits (Enrollment and 3-month) will be conducted by research staff **by telephone**. The following procedures will be included.

- Review and update locator information
- Self-reported study product adherence assessment

Self-reported PrEP adherence for all participants will be assessed using both a visual analogue scale (VAS) and a new 3-item self-report measure. The VAS is empirically validated, consistently under-reports adherence, but effectively measures a “difference” in adherence that changes in response to an intervention. The 3-item adherence self-report scale showed good psychometric characteristics and good construct validity when compared with an drug monitoring standard. Two self-report adherence measures are often recommended.

- PrEP discussion
- Autonomy supportive adherence counseling
- SMS reminder customization

Experimental arm participants will have an opportunity to change the parameters of the SMS reminders.

- HIV/ STI behavioral risk-reduction counseling

After the standard risk-reduction counseling, the participants will be invited to visit the harm reduction site to receive supplies.

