#### PrEP persistence

PrEP persistence is defined as the time from PrEP start to PrEP discontinuation. A PrEP discontinuation is considered to have occurred if a participant self-reported to miss the PrEP doses for 30 or more consecutive days, for reasons other than a medication hold instituted by a clinician.

**Secondary Endpoints:** The secondary endpoints of this study include the following:

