## APPENDIX II – SURVEY BATTERY AND OTHER FORMS

### Forms filled by the PNs:

- Initial PrEP adherence readiness assessment
- Care Coordination Measurement Tool

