### Forms filled by the interviewer:

- PrEP Adherence (visual analog scale [VAS] and 3-item screener, additional block for those who discontinue)
- Client Perception of Coordination Questionnaire (24-items)
- Health Care Climate Questionnaire (15-items/ 5-item short form)
- Care Transition Measure (15-items/ 3-item short form)
- Health Care Climate Questionnaire
- Perceived HIV risk and severity
- Depression scale
- Perceived Competence for PrEP Use
- PrEP Self-Regulation Questionnaire
- PrEP/PEP Awareness
- Satisfaction with PrEP provision, medicines
- Side effects (at baseline – anticipation of SEs, at follow-up impact of SE on adherence)
- Sexual and injection risk behavior (n days injected, n days shared equipment, n days of sex, n days sex without condoms, n partners [of them PLWH])
- Social support (do you plan to tell anyone, have you told anyone, did he help, if did not – why?)
- Stigma (related to PrEP, ARV, PWID)
- Substance use inventory (short)
- Use of reminders (what type of reminders you use)

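### The protocol assigns self-reported adherence both to the navigator who coaches adherence and to research staff, and persistence rests on that self-report alone

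*Protocol*

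**What the plan says.** Three parts of the protocol bear on who collects self-reported adherence.

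- **Appendix I** has a row "Self-reported study product adherence assessment (PN", where PN stands for PrEP navigator. It is marked for Months 1 and 3, the telephone months 2, 4 and 5, Month 6, and interim visits.
- **Section 5.4** says the telephone assessments "will be conducted by research staff". Self-reported adherence is on their list of procedures.
- **Appendix II** puts "PrEP Adherence (visual analog scale [VAS] and 3-item screener, additional block for those who discontinue" among the interviewer's forms. Under "Forms filled by the PNs" it lists only the readiness assessment and the care coordination tool.

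Section 5.2 separates the roles. For the survey, a research-staff task, it says "Structured interviews will be administered by an experienced interviewer using the questionnaire designed by study team". The navigators' work falls under intervention staff, and of adherence counselling it says "This counseling is delivered one-on-one by PrEP navigators during the study visits".

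Section 7.1 describes the trial as open-label. Among the primary endpoints it defines PrEP discontinuation as occurring when a participant "self-reported to miss the PrEP doses for 30 or more consecutive days", other than during a hold ordered by a clinician.

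**The concern.** Persistence has no source other than what the participant says about missed doses. The VAS and the 3-item scale are also self-report. Under Appendix I, the person who asks is the one whose job is to improve the answer. Participants may be reluctant to tell their adherence coach that they stopped, so discontinuations could be missed or dated late and self-rated adherence could be too high.

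The second risk is inconsistency. A site working from the schedule table would use the navigator, and a site working from Section 5.4 or the form list would use research staff. The collector could then differ by site or by month without anyone recording it, which adds avoidable measurement variation to an outcome listed under the primary endpoints.

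**Working it through.** No formula applies, because the point rests on no sample size, power or event figure. The check is a comparison of the texts.

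**Who collects, by contact**

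| Contact | Appendix I | Section 5 text | Appendix II (all contacts) |
|---|---|---|---|
| Months 1, 3, 6 | Navigator | 5.3 lists the task and names no one | Interviewer |
| Months 2, 4, 5 (telephone) | Navigator | 5.4: research staff | Interviewer |
| Interim visits | Navigator | 5.5 names no one for this task | Interviewer |

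The scheduled follow-up contacts number 3 + 3 = 6. Appendix I conflicts with Appendix II at all six, and with Section 5.4 as well at three of them. Section 5.3 settles nothing for Months 1, 3 and 6.

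**Is the interviewer a third role?** No. Section 5.2 lists the interviewer's survey among the research-staff tasks. Two roles are in conflict: navigator and research interviewer.

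**Is the navigator label meaningful?** The row just above in Appendix I, the initial readiness assessment, carries the same label. There it agrees with Section 5.2 and with Appendix II. On the adherence row it agrees with neither Section 5.4 nor Appendix II.

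**Which outcomes depend on the collector?**

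- Persistence depends on it fully, by its definition in Section 7.1.
- The VAS and 3-item measures depend on it, and so do the correlation and kappa comparisons with drug levels in Section 7.3.1.
- The binary high-adherence outcome does not. Section 7.3.1 defines it by a tenofovir threshold of 700 fmol/punch in dried blood spots.

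**Can drug levels check the monthly reports?** Only in part. No blood spot is scheduled in the telephone months, and Section 5.2 allows testing of only a subset of samples.

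**Would relabelling the row separate the two tasks?** Not at Months 2, 4 and 5. Section 5.4 places the PrEP discussion, the adherence counselling and the SMS customization inside the same research-staff calls, whereas Section 5.2 gives the counselling to navigators. As written, research staff could both ask and counsel on those calls.

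**The case against.** The strongest reply is that this is a stray label. Appendix II is specific about forms, and Appendix I places the row in its administrative and behavioural block, which Section 5.2 describes as research-staff work. Detailed instructions are left to operating procedures. Much of this stands: the documents lean towards the interviewer. The block heading does not decide it, however, because the readiness assessment sits in the same block and is a navigator task. Appendix I is also the table that sites are likely to work from.

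A second reply is that self-report in an open-label trial carries bias whoever asks. That also stands. The change reduces an avoidable part of the bias and does not remove it.

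A reader might infer three stronger points, and the documents do not support them.

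- **Bias in favour of SMS.** This needs over-reporting that differs by arm. Adherence counselling goes to participants in both arms, so collection by navigators does not by itself create a difference. Navigators can know the arm, and SMS customization is listed with intervention-staff work, so a difference is possible. It is not shown.
- **A size taken from Section 1.1.** The background reports self-reported against measured adherence of 51% and 41% in one study (51 − 41 = 10 points) and 67% and 49% in another (67 − 49 = 18 points). It does not say who collected those self-reports, so the gaps cannot show what a navigator adds over an interviewer.
- **A contradiction over the VAS.** Section 5.4 says the VAS "consistently under-reports adherence". The background figures name no instrument, so they do not refute a statement about the VAS in particular.

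**Conclusion.** The point holds as an inconsistency with a measurement consequence. Two roles are assigned the same assessment, and the conflict reaches every scheduled follow-up contact. Under one reading, the adherence coach collects the only data that define persistence. The direction of the risk within an arm, towards over-reporting, is a judgement about how people answer someone who is coaching them. The documents give no figure for it, and no effect on the comparison between arms can be claimed. The blood-spot binary analysis stands whichever role collects the self-report. The continuous alternative in Section 7.3.1 would be touched only if it uses the self-report scales, which that section does not say.

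The correction should be made before enrolment, because the collector cannot be changed afterwards and persistence has no other source.

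**What to change.** 1. In Appendix I, change the label on this row from navigator to research interviewer, in line with Appendix II. The row also covers interim visits.
2. In Section 5.3, state that the interviewer who already administers the survey at Months 1, 3 and 6 completes the VAS, the 3-item scale and the discontinuation block before any counselling at that visit.
3. In Section 5.4, reconcile with Section 5.2 who counsels on the Month 2, 4 and 5 calls. Require the adherence items to be completed before any counselling or SMS customization on the call. If the same person is to ask and to counsel, this order is the remaining safeguard.

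The cost is one table label, a few sentences and a fixed order of procedures at each contact. No extra staff are needed: the interviewer already holds this form and already sees participants at Months 1, 3 and 6, and research staff already make the calls. No blinded assessor is required.

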## APPENDIX II – SURVEY BATTERY AND OTHER FORMS

### Forms filled by the PNs:

- Initial PrEP adherence readiness assessment
- Care Coordination Measurement Tool

### Forms filled by the interviewer:

- PrEP Adherence (visual analog scale [VAS] and 3-item screener, additional block for those who discontinue)
- Client Perception of Coordination Questionnaire (24-items)
- Health Care Climate Questionnaire (15-items/ 5-item short form)
- Care Transition Measure (15-items/ 3-item short form)
- Health Care Climate Questionnaire
- Perceived HIV risk and severity
- Depression scale
- Perceived Competence for PrEP Use
- PrEP Self-Regulation Questionnaire
- PrEP/PEP Awareness
- Satisfaction with PrEP provision, medicines
- Side effects (at baseline – anticipation of SEs, at follow-up impact of SE on adherence)
- Sexual and injection risk behavior (n days injected, n days shared equipment, n days of sex, n days sex without condoms, n partners [of them PLWH])
- Social support (do you plan to tell anyone, have you told anyone, did he help, if did not – why?)
- Stigma (related to PrEP, ARV, PWID)
- Substance use inventory (short)
- Use of reminders (what type of reminders you use)

### Detailed description of selected instruments:

#### PrEP Adherence Self-Regulation Questionnaire (15-items)

We will use a modified version of the Treatment Self-Regulation Questionnaire (TSRQ) to assess participants' reasons for using PrEP if self-determined—whereby higher self-determination scores reflect greater internalization of the target behavior and increased likelihood of adherence. The TSRQ uses a 7-point Likert scale and has been modified in previous studies to address adherence to antiretroviral medication and other specific health behavior targets such as diet and exercise. The TSRQ was shown to have adequate internal consistency with alphas ranging from (.85 to .93) across several studies.

#### Health Care Climate Questionnaire (15-items/ 5-item short form)

The HCCQ uses a 7-point Likert scale to assess the degree to which participants perceive their clinical team to be autonomy supportive. Higher scores indicate greater perceived autonomy support. The HCCQ uses the concept of autonomy support, from self-determination theory, to characterize the client-centeredness of clinical environments, hypothesizing that autonomy-supportive (client-centered) clinical environments facilitate self-determined motivation for the adoption of target health behaviors. The  $\alpha$  coefficient for the internal

consistently of the HCCQ is > 0.90.

Client Perception of Coordination Questionnaire (24-items)

We will use the CPCQ to measure the client's perspective whether the care they received over time was client-centered and coordinated between health care providers. The CPCQ demonstrated good internal consistency ( $\alpha = 0.92$ ). CPCQ has six subscales with alphas ranging from 0.31 to 0.86. We will use the four subscales with good internal consistency and adapt them for structure of the C4 model: (1) acceptability of care coordination, (2) receipt of self-perceived needed care, (3) perception of clinical care provider, (4) perception of psychosocial care provider. This reduces the item count from 31 to 24. While the CPCQ is the longest measure within the battery, it exhibited high completion rates (>95%) in the study in which it was developed.

Care Transition Measure (15-items/ 3-item short form)

The Care Transition Measure (CTM) uses 4-point Likert scale to assess quality of transition from hospital care to community-based care or home. CTM will be adapted to assess client-centered transition from PrEP management in the C4 model to community-based clinical supervision of PrEP. The CTM demonstrated high-internal consistency and reliability, and adequate convergent validity with a validated measure of client-perception of the quality of hospital discharge/transfer process. Spearman inter-item correlations were between 0.35 and 0.75 which indicate that the scales are conceptually similar but are not measuring identical constructs.

The following items will be collected on a CRF whenever care coordination is performed:

Care Coordination Measurement Tool (CCMT)

We will measure the activities involved in providing client-centered care coordination for PrEP using a modified version of the CCMT. The CCMT was developed based on national expert panel recommendations for care coordination measurement. Among the items captured on the CCMT include: (1) client complexity level, (2) focus of the encounter (e.g., clinical/medical, legal, mental health, referral management, social service), (3) type of coordination needed, (4) services/activities rendered, (5) time-spent on coordination activities, and (6) outcome of coordination. The CCMT is designed for use by all personnel involved in a particular client-centered care coordination evolution and has been successfully used in previous studies. The CCMT will allow us to obtain robust characterizations of care-coordination encounters for use in addressing our secondary objectives.

